Clear and refutable hypotheses of the R61 are: H1a) UE or UE&CIT will lead to significantly greater gains in CS than will ACCT and/or H1b) CIT or UE&CIT will produce significantly greater improvements in PO compared to ACCT. The **Go Signal** for continuing to the R33 will be a differential improvement, with an effect size of at least d=0.4, favoring UE or UE&CIT compared to ACCT on the psychophysical and/or electrophysiological CS task, *and/or* CIT or UE&CIT compared to ACCT on the JOVI and/or Ebbinghaus task. If a "go" signal is obtained, results of the R61 will be used to identify the most effective and efficient treatment (UE, CIT, or UE&CIT), and duration/dose, for use in the R33.

**Clear and refutable hypotheses of the R33 are:** H1) The optimal treatment identified in the R61 (e.g., UE&CIT) will be more effective than the control treatment (ACCT) in improving CS or PO in a new and larger sample; and H2) Improvements in target function will be related to changes on visual cognitive (i.e., visual learning and memory, reading), social cognitive (i.e., facial emotion recognition) and functional capacity measures. If the hypotheses in the R33 are confirmed, the results will inform the design of a later RCT to assess the efficacy of a visual remediation treatment for schizophrenia on a wider range of outcome variables. Instructions for the R33 state that it "should not be powered as strong tests of clinical efficacy but rather should test the link between... target engagement and functional outcome." Therefore, while we expect the correlations for R33 Aim 2 to be statistically significant, we do not hypothesize what the effect sizes will be. However, we would power a subsequent study based on the observed effect sizes in the R33.

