
### D. Approach

#### D.1 Preliminary Data

UE pilot study: Pilot data from patients with schizophrenia at the Nathan Kline Institute (NKI) and Rutgers show good retention with 6 of 7 patients (86%) completing at least 30 sessions. This is similar to previous single-site cognitive remediation studies and to an average retention rate of 87% in a metaanalysis of 40 cognitive remediation studies in schizophrenia. This also matches the 93% retention rate of UE studies in healthy young adults carried out by [name] (co-investigator and developer of UE). Preliminary data show UE is well tolerated, and even enjoyed, as described in our recent publication. Across participants, CS improved 32%, with an increase in the peak contrast spatial frequency of 1 cycle/degree (pre-training peak spatial frequency of  $3.14 \pm 0.24$  vs. post-training of  $4.15 \pm 0.70$ , p=.14, d=0.96). Additionally, patients improved on contour integration (p=.11, d=0.85). With such a small sample (N=6), our results were not statistically significant. However, the magnitude of CS improvement is similar to that from published studies of UE.

UE findings in non-psychiatric samples: In previous research on UE conducted by [name], CS improved in healthy normal-sighted individuals after  $\sim$ 30 sessions of training, with effect sizes ranging from

d=1.6 for LSF to 0.63 for HSF stimuli. In another study, college baseball players displayed significant improvements in CS (Fig. 1) and batting average $^{70}$ after UE training, with effect sizes ranging from d=0.34 to 0.59 (with the lowest effect size for CS to HSF stimuli). Additionally, university students demonstrated improved reading ability after UE training. Specifically, reading acuity improved an average of 13% (d=0.38), moving from a pre-training mean logMAR acuity of -0.06 to a post training value of -0.11, (SD=0.02). Reading speed improved 13% (d=0.57), moving from a pre-training mean value of 240.0 words/minute to a post-training value of 270.6 words/minute  $(SD=8.28)^{21}$ . In addition, older adults with presbyopia

displayed improved CS after undergoing UE training. It is important to note that in the studies of UE in which

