# D.3 R61 Phase

Aims: (i) To evaluate the effects of UE and CIT on the CS and PO targets, respectively; (ii) to determine if the criterion for continuing to the R33 phase is met; and (iii) if the criterion is met, to determine the most effective intervention condition and optimal duration of treatment, to inform the R33 study design.

Study design: 80 subjects will be enrolled in this study: 20 per arm. 40 will be recruited at each site (Rutgers and NKI). The intervention will continue for 40 sessions, with targets assessed before training, after every 10 sessions, and at 6 months post-training for a total of 6 visual assessments. With 3 sessions per week, the intervention will take between 13-14 weeks. Each site will enroll ~ 2 participants/month, beginning after the first half of Y1, which is similar to what Keefe et al. estimated as a "reasonable rate of recruitment for a largescale efficacy trial" of cognitive remediation. Because, at the 6-month follow-up, nearly all patients are expected to still be in the partial hospital program, or an outpatient program (at Rutgers), or on inpatient units at the Rockland Psychiatric Center (RPC) or NKI, we expect attrition to be minimal. However, several methods, including monthly phone calls (see Recruitment and Study Timeline), will be used to maximize retention. For the R61 and R33, training sessions will be run in small groups by front-line staff who have already received training in these interventions, or whom we will train, with no more than a 3:1 participant:staff ratio. Randomization: Subjects will be randomly assigned, within site, to one of the 4 conditions (UE&ACCT, CIT&ACCT, UE&CIT and ACCT&ACCT) in a ratio of 1:1:1:1. The treatment assignment will be made after a subject has met all entry criteria and completed baseline testing, to avoid bias.

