Milestones (Go/No-Go Criterion): We will proceed to the R33 phase if: 1) the UE-related effect size (i.e., the effect size of the difference between the UE&ACCT (or UE&CIT) and ACCT&ACCT groups in the degree of change in CS) is greater than or equal to Cohen's d=0.4 for **either** the psychophysical **or** ssVEP CS task: and/or 2) the CIT-related effect size (i.e., the effect size of the difference between CIT&ACCT (or UE&CIT) and ACCT&ACCT groups in the change on **either** of the PO tasks) is greater than or equal to d=0.4. Pre-post change scores for CS and PO target assessments will be calculated for each individual and used to determine effect sizes between groups. We will not control for baseline values consistent with recommendations to use "straight" change scores when examining cognitive change across two time points.

Rationale for our effect size choice: The effect size criterion we have chosen for the R61 "go" signal (d=0.4)

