# Sample size determination:

The sample size of the R61 study (n=20/group) was selected to ensure that when the true size of the effect of UE or UE&CIT on the CS target, or CIT or UE&CIT on the PO target, is d=0.4, the 95% confidence interval (CI) for the effect size does not contain zero. Given data on the CS measure over time in the UE pilot study described earlier, a 95% confidence interval for an effect size of magnitude 0.4 is between .02 and .91. Since the observed effect size in that pilot data was actually much larger, 0.96, we are confident that we will be adequately powered to detect a meaningful effect. Since patients also improved on a measure of contour integration (d=0.85) in the pilot study, even though training was focused only on CS (our low-level visual target), setting the effect size at d=0.4 for both CS and PO seems reasonable. Note that although contour integration improved without PO training in the pilot study, this was unlikely due to practice effects on the test alone since two prior large studies did not find practice effects on the JOVI, in either healthy controls or

patients, over two or three repeated presentations separated by days or weeks, and a third study found improvements only with daily exposure to two versions of the task, and this did not occur for the schizophrenia group until the third day. Subjects who do not complete all 40 sessions of training will be invited to complete a "post-treatment" assessment after their last session; for non-completers who decline to participate in a post-treatment evaluation, the last post-baseline assessment will be used, unless the participant dropped out before the 10th session (the time of 1st post-baseline assessment), in which case his/her data will be not be used in the analyses. In such cases, we will recruit additional participants to reach the target sample size. We expect minimal dropout since most participants will be long-stay inpatients or partial hospital patients who are present on a nearly daily basis. For any dropout that does occur, we expect rates to be uniform across conditions, given that we have designed all conditions, including the active control, to be similarly engaging. Sufficient patients are available at both sites to recruit new subjects to replace any who discontinue. D.4 R33 Phase

[figure not shown]

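### R61's carry-forward and discard-and-replace rules can shift each arm's effect size; the go decision moves little unless early, response-related dropout is concentrated in the active arms

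*Combined protocol and SAP*

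**What the plan says.** Section D.3 (Randomization) places assignment after eligibility and baseline: "The treatment assignment will be made after a subject has met all entry criteria and completed baseline testing, to avoid bias". Targets are then measured after every 10 sessions up to 40, and at 6 months.

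The go criterion (D.3, Milestones) rests on change scores: "Pre-post change scores for CS and PO target assessments will be calculated for each individual and used to determine effect sizes between groups". It does not say that the post value is the one at session 40. A go needs d of at least 0.4 on any one of several contrasts. Section B describes the CS half as an effect "favoring UE or UE&CIT compared to ACCT on the psychophysical and/or electrophysiological CS task", and the PO half has the same form.

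Non-completers are dealt with in D.3 under Sample size determination. All are invited to an exit assessment. Then, "for non-completers who decline to participate in a post-treatment evaluation", the rule is that "the last post-baseline assessment will be used, unless the participant dropped out before" session 10, "in which case his/her data will be not be used in the analyses". The plan adds: "In such cases, we will recruit additional participants to reach the target sample size". Read literally, the discard covers those who leave before session 10 and also decline the exit assessment.

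The same section expects little dropout, at uniform rates across conditions. It sets no R61 dropout rate and no sensitivity analysis. Intention to treat is stated only in D.4, for R33.

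**The concern.** Two different errors can enter the effect size.

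- **Carry-forward.** A score from session 10, 20 or 30 stands in for the end of training. If benefit builds with sessions, this understates the session-40 effect.
- **Discard and replace.** People are removed for something that happened after assignment. If those who leave an active arm early are those who would not have benefited, the remaining group looks better than the arm as randomised.

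The effect size has two uses: the go decision, and the choice of R33 treatment in D.3, which looks for a significantly larger effect on at least one target and then for the earliest asymptote. The longitudinal models in D.3 serve trajectory and treatment choice, not the go estimate. The discard is worded for the analyses in general, so it would reach those models too.

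**Working it through.** **Inputs from the documents.** 20 per arm, four arms, 1:1:1:1 (D.3). Go threshold d = 0.4 (D.3). Retention in D.1: "6 of 7 patients (86%) completing at least 30 sessions", 87% in a meta-analysis, and 93% in healthy young adults. Non-completion is therefore 1/7 = 14%, 13% or 7%. Correlation between the two CS tasks: 0.41 (D.6.b).

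**Assumptions, not in the documents.** The early/late split of leavers; whether leaving is related to response; correlation 0.41 also within PO and 0.2 between CS and PO; every leaver declines the exit assessment.

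**Yardstick.** The session-40 effect in all randomised participants, set at d = 0.40. The plan gives no figure of its own for dropout bias, so there is none to reproduce.

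**1. Carry-forward, leaving unrelated to outcome, linear gain.** With a share p carried forward from a point where a fraction f of the gain has accrued, d = 0.40 × [1 − p(1 − f)].

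| Last data at | f | p = 0.14 | p = 0.07 |
|---|---|---|---|
| session 10 | 0.25 | 0.40 × 0.895 = 0.358 | 0.40 × 0.9475 = 0.379 |
| session 20 | 0.50 | 0.40 × 0.930 = 0.372 | 0.40 × 0.965 = 0.386 |
| session 30 | 0.75 | 0.40 × 0.965 = 0.386 | 0.40 × 0.9825 = 0.393 |

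There is no shift if gains plateau by session 10, or if late active-arm leavers would have gained only what controls gain.

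**2. Discard and replace.** If a share q of the active arm leaves early and would have gained no more than controls, the rest must carry the whole effect: d = 0.40/(1 − q). For q = 0.05, 0.10 and 0.15 this is 0.421, 0.444 and 0.471. There is no shift if leaving is unrelated to outcome.

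**3. Probability of go.** There are eight contrasts: two arms on two CS tasks and two arms on two PO tasks (2 × 2 + 2 × 2), all against one control arm. Go means that at least one observed d reaches 0.4. The simulations use four arms of 20.

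| Mean d in every active contrast | Probability of go | Single contrast |
|---|---|---|
| 0.372 | 0.95 | 0.47 |
| 0.40 | 0.96 | 0.50 |
| 0.444 | 0.98 | 0.56 |

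These values sit near the ceiling, so the table cannot by itself show that the decision is insensitive. Lower true effects have to be examined as well.

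- **Equal 13% dropout in all arms:** 0.47 to 0.49 against 0.48 at d = 0; 0.78 to 0.82 against 0.80 at d = 0.2; 0.95 to 0.97 against 0.96 at d = 0.4. At 25% it stays within about 3 points.
- **13% dropout in the active arms only, all before session 10:** each active contrast rises by about 0.05 if the correlation between staying and responding is 0.3, and by about 0.10 if it is 0.6. Shifts of that size move the probability of go from 0.48 to about 0.56 or 0.65 at d = 0, and from 0.80 to about 0.86 or 0.90 at d = 0.2.
- **13% in the control arm only:** the opposite sign, down to between 0.40 and 0.33 at d = 0.
- **Source of the movement:** carry-forward alone, with 13% response-related late dropout in the active arms, moved the probability of go by only about 1 point. Discard and replace is the main driver.

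**4. Treatment choice.** With 13% early, response-related dropout in one active arm only, that arm's d moved by 0.05 to 0.10 and the other two did not move. What this does to the choice itself was not quantified.

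**The case against.** The strongest defence has four parts.

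- **Dropout should be low and even.** The plan offers every leaver an exit assessment, expects few leavers because most participants are inpatients or attend almost daily, and designed the control to be equally engaging. This stands as far as it goes: under uniform dropout the go decision hardly changes. It remains an expectation, with no planned check behind it.
- **The shifts are small beside sampling error.** The largest simulated shift was 0.067, against a standard deviation of d of 0.32. This also stands, and is why the point is minor. A bias that pushes all active contrasts the same way still adds up over eight chances to pass.
- **Treatment choice uses longitudinal models.** The documents do not say that carried-forward scores enter those models, and shifts common to the active arms largely cancel. In one check with true effects of 0.4, 0.4 and 0.6 and 14% uniform late dropout carried forward, the chance of picking the better arm went from 0.60 to 0.58. Dropout confined to one arm would not cancel.
- **A mixed model is no cure.** Over nine simulated scenarios its mean absolute error against complete data was 0.022, against 0.021 for the plan's rule. This stands: the model alone is not enough, hence the sensitivity estimate in the fix.

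A reader might infer that the discard rule also governs R33, because D.4 calls its attrition procedures identical to those of R61. That remark is attached to the 6-month follow-up and can equally refer to the retention measures in D.3, while D.4 states intention to treat. It calls for a clarification only. A reader might also count an exit assessment as an imputed value; it is an observed outcome, and the only gap is the session at which it is analysed.

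**Conclusion.** The concern holds with conditions, at minor severity. The rules can move a session-40 effect of 0.40 down to about 0.36 (late leavers, linear gain, leaving unrelated to outcome, 14%) or up to about 0.47 (15% active-arm early leavers who would not have responded). The direction is not fixed, so the documents do not support a claim that the rules always favour the treatment.

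Two broader readings also fail. One is that the go decision is unreliable because of these rules: it changes by about 2 points or less under uniform 13% dropout, and is near its ceiling if the true effect is about 0.4. The other is that the go decision is safe because any of eight contrasts suffices: at a true effect of 0 or 0.2, early response-related dropout concentrated in the active arms raises the probability of go by roughly 6 to 17 points (0.86 − 0.80 to 0.65 − 0.48).

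These figures are a range, not a forecast. The documents do not give the timing of leaving, the reasons for it, or the correlations between CS and PO changes. The pilot's 14% is one person in seven.

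**What to change.** In D.3:

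1. Define the go effect as the session-40 contrast in all randomised participants.
2. Estimate it with a repeated-measures model using all available assessments, with each exit assessment entered at the session where it was taken. Do not constrain baseline means to be equal, since D.3 declines baseline adjustment. Divide by the standard deviation of observed baseline-to-session-40 change.
3. Keep replacement recruitment if wanted, but count those replaced in their assigned arm. Report dropout by arm and by session of leaving.
4. Add one sensitivity estimate that gives active-arm leavers the control-arm mean change, over the same standard deviation. State in advance that the main estimate decides go, and that a result with the two estimates on either side of 0.4 is reported as not robust.

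In D.4, state that the R61 discard rule does not apply to R33, in line with intention to treat.

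**Cost.** Analysis wording and one extra estimate; longitudinal models are already planned. Simulation showed no loss of precision (standard deviation of d 0.30 for the model, 0.32 for the plan's rule). The model relies on data missing at random and cannot correct for early leavers with no post-baseline data. It reads high if leavers are non-responders (0.45 against 0.41 for late leavers at 14%). The sensitivity estimate reads low if leaving is unrelated to outcome (0.35 against 0.40). Reported together, they show the range.

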Aims: (i) To replicate and extend R61 results supporting initial visual target engagement using the optimal R61 treatment, in a new and larger sample; and (ii) to determine if visual target engagement is associated with improvements in specific cognitive (i.e., visual working memory, visual learning and memory, reading) and social cognitive (*i.e.*, facial emotion recognition) outcomes, as well as with changes in functional capacity. Study design: The R33 will be a two parallel-arm RCT comparing the optimal R61 treatment to the control (ACCT) treatment. 100 subjects will be enrolled over 3 years, 50 from NKI and 50 from Rutgers. Visual and clinical outcome assessments will be conducted at baseline, and at intervals determined based on R61 results, including a 6-month follow-up (with attrition considerations and procedures identical to the R61 (see D.3). **Randomization:** Subjects will be randomly assigned, within site, to the optimal or control treatment in a ratio of 1:1. Treatment assignment for eligible subjects will occur after completion of baseline testing, to avoid bias. Assessments: Visual Targets and Cognitive, Social Cognitive, and Functional Capacity. No matter which intervention is used for the R33, visual tests will include both tests of CS, and both tests of PO used in the R61. See below (section D.6.c) for descriptions of the cognitive, social cognitive, and functional capacity measures. **Data analysis:** An intention to treat approach to data analysis will be used in this clinical trial. For all analyses. statistical significance will be defined as p < 0.05, unless specified otherwise. Bonferroni corrections will be applied to multiple testing, as appropriate. H1: The optimal R61 treatment will be more effective than the control treatment (ACCT) in improving CS and/or PO test scores (to be determined based on the R61 outcome). This will be tested using a linear mixed effects model in which the values of the target(s) at each time point are modeled as a function of treatment group (experimental, control), time, time x group, and potential moderators and mediators (e.g., age). We will use Akaike's Information Criterion (AIC) as the deciding metric to determine the optimal model to account for within-subject correlations between repeated measures (e.g., autoregressive of order 1, AR(1), which assumes stronger within-person correlation for measurements closer in time, or other structures). If the time x group interaction is significant, we will use model-based estimation procedures to estimate the magnitude of the effect. We will also explore differential effects of the treatment on CS vs. PO. H2: Improvements in visual processing, as observed in CS and/or PO (based on R61 results), will be related to changes on specific cognitive (i.e., visual working memory, visual learning and memory, reading), social cognitive (i.e., emotion recognition), and functional capacity measures. We will assess correlations between visual target scores and cognition, social cognition, and functional capacity, and also evaluate whether changes in the target(s) either mediate or moderate treatment effects on these outcomes. An approach and computational tool described by Hayes will be used to model any mediation and /or moderation effects, including indirect effects in models that involve mediation. Sample size determination: The sample size for the RCT in the R33 phase was selected to ensure sufficient power to detect medium effects of the experimental intervention on the target(s). For Aim 1 of the R33, 50 subjects per condition allows 80% power for a 2-tailed test with  $\alpha$ =0.05 to detect d=0.57. For Aim 2, with n=50 in the active perceptual training group, correlations of at least r=0.38 between changes in performance on target measures (CS and/or PO) and changes in cognitive, social cognitive, and functional capacity can be detected with 80% power using a 2-tailed test with  $\alpha$ =0.05. Also, for Aim 2, n=50 (i.e., active perceptual intervention only) allows for detecting a correlation of r=0.43 when making a strict Bonferroni adjustment for 3 outcomes (2-tailed  $\alpha$ =0.017), and r=0.51 when correcting for 15 outcomes (2-tailed  $\alpha$ =0.003). In accordance with instructions that the R33 "should not be powered as a strong test of clinical efficacy...", our focus on effect size is exploratory and not confirmatory. We will use our observed effect sizes to power a later RCT. D.5 Interventions

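### R33 multiplicity: Holm's step-down method would control the same family-wise error as the planned Bonferroni correction and recover a few points of power whenever two or more effects are real

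*Combined protocol and SAP*

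**What the plan says.** All of this concerns the R33 phase (D.4 of the combined protocol and SAP).

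- Data analysis: "statistical significance will be defined as p < 0.05, unless specified otherwise", followed by "Bonferroni corrections will be applied to multiple testing, as appropriate". No family of tests is defined and no step-down method is mentioned.
- Sample size, Aim 1: "50 subjects per condition allows 80% power for a 2-tailed test with" alpha 0.05 "to detect d=0.57". This figure carries no multiplicity adjustment.
- Sample size, Aim 2: "with n=50 in the active perceptual training group", the plan can detect "correlations of at least r=0.38 between changes in performance on target measures" and changes in the other outcomes, at unadjusted alpha 0.05. It then gives r=0.43 "when making a strict Bonferroni adjustment for 3 outcomes" (alpha 0.017) and r=0.51 for 15 outcomes (alpha 0.003).
- Section B (R33 hypotheses) expects the Aim 2 correlations to reach significance but declines to state their size. D.4 describes the effect-size focus as exploratory.
- D.6.c lists the non-visual-target outcomes with a count of scores for each: MCCB 8, MNREAD 3, ER-40 1, UPSA-2 1.

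**The concern.** Single-step Bonferroni tests every outcome at 0.05/k, however many other outcomes have already been rejected. Holm tests the smallest p-value at 0.05/k, the next at 0.05/(k-1), and so on up to 0.05, stopping at the first failure. It has the same family-wise bound and, like Bonferroni, assumes nothing about dependence. It can therefore only add rejections.

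H2 names several outcomes that should track improvement in the visual target, so more than one non-null correlation is plausible, and that is the situation in which Holm helps. Aim 2 uses only the 50 participants in the active arm, so power is limited. The plan gives no reason, such as a need for simultaneous confidence intervals, for preferring the single-step form. At stake is some avoidable loss of power for the second and later true effects. Validity is not at stake.

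**Working it through.** **1. The plan's own figures.**

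Aim 1: two-sample t-test, 50 per arm, two-sided alpha 0.05, d=0.57. Power is 80.6% (81.3% by the normal approximation) and the smallest d at 80% power is 0.566. The plan's figure reproduces.

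Aim 2: by Fisher's z, power ≈ Φ(atanh(r)·√(n−3) − z(1−α/2)), with n=50 and √47=6.856.

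- r=0.38, α=0.05: 0.4001×6.856=2.743; 2.743−1.960=0.783; power 78.3%.
- r=0.43, α=0.017: 0.4599×6.856=3.153; 3.153−2.387=0.766; power 77.8%.
- r=0.51, α=0.003: 0.5627×6.856=3.858; 3.858−2.968=0.890; power 81.3%.

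Sampling r directly under bivariate normality gives 79.2%, 78.6% and 81.7%. All are within 2 points of 80%, so the printed r values stand. The alphas are rounded forms of 0.05/3=0.0167 and 0.05/15=0.0033.

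**2. Why Holm cannot do worse.** If p ≤ 0.05/k for an outcome, every smaller p-value also meets 0.05/k, and Holm's thresholds start at 0.05/k and only increase. So every Bonferroni rejection is a Holm rejection. The first Holm step is Bonferroni, so the chance of at least one rejection of any kind is identical.

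**3. Size of the gain.** Fisher-z statistics were simulated with n=50, family-wise two-sided alpha 0.05, and the plan's r values used as the true correlations. Two inputs are assumptions because the documents give neither: the equal correlation among test statistics (0.2 and 0.5) and the number of outcomes with a real effect.

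| Outcomes | True r | Real effects | Bonferroni, power per true outcome | Holm, power per true outcome |
|---|---|---|---|---|
| 3 | 0.43 | 1 | about 78% | about 78% |
| 3 | 0.43 | 2 | about 78% | about 81% |
| 3 | 0.43 | 3 | about 78% | 84-85% |
| 15 | 0.51 | 1 | 82% | 82% |
| 15 | 0.51 | 5 | 82% | 84% |
| 15 | 0.51 | 7 | 82% | 85% |
| 15 | 0.51 | 10 | 82% | 87% |

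The chance of at least one significant true effect agreed between methods to within about 0.001 in every row. No Bonferroni rejection was lost under Holm, and simulated family-wise error under Holm stayed below 0.05.

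A second simulation, from raw data with residual correlation 0, 0.3 or 0.5 among outcomes, agreed: about 82% with two of three real, 85-87% with three of three, and 85-86% with seven of 15.

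**4. What drives the gain.** It is the number of real effects, not correlation among outcomes. With all three effects real, the chance of detecting all three rises from 51% to 70% (19 points) when the correlation is 0.2, and from about 57% to 74% (about 16 points before rounding) when it is 0.5. Higher correlation makes the gain smaller.

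**5. Family size.** D.6.c lists 8+3+1+1=13 scores, whereas the power text corrects for 3 or for 15. Holm orders the p-values of a complete family, so the family must be listed before it can be run. Bonferroni also needs k.

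**The case against.** The strongest reply is that nothing here is wrong: Bonferroni is valid, the printed detectable effects reproduce, and R33 is meant to estimate effect sizes for a later trial, which Holm does not alter. All of that stands, and it keeps the priority low.

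Three stronger readings are tempting and are not supported.

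- A reader might take three outcomes all at r=0.43 as the plan's own scenario. D.4 gives 0.43 only as the correlation detectable for one outcome at alpha 0.017, and section B declines to hypothesise Aim 2 effect sizes. Three of three is the most favourable case for Holm at k=3.
- A reader might quote the rise in the chance of detecting all three effects (51-58% to 70-74%) as the effect of the change. No R33 decision requires every outcome to be significant.
- A reader might expect most of 15 outcomes to be non-null. H2 is selective: visual working memory (1 score, through the MCCB working memory domain), visual learning (1), reading (3), emotion recognition (1) and functional capacity (1) make about 7 of the 13 listed scores. Sections C and D.6.c also plan to contrast visual with non-visual cognition. With 7 of 15 real, the gain is about 3 points.

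It is also fair to say that changing the method's name alone leaves the families undefined. That is met by listing them in the same edit.

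**Conclusion.** The point holds as a low-priority efficiency improvement. Holm gives the same family-wise protection with no additional assumption and never rejects less. The gain in power per true outcome is nil with one real effect, about 3 points with two of three or seven of 15 real, about 5 points with ten of 15, and about 6 to 8 points with three of three. These sizes rest on n=50 with complete data, true correlations equal to the plan's detectable values, a correlation of 0.2 to 0.5 among test statistics, and assumed numbers of real effects. That Holm is never worse rests on none of these. If H1 is tested on a single target, nothing changes there.

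**What to change.** In D.4, before any R33 data are seen, replace the Bonferroni sentence with Holm step-down at family-wise two-sided alpha 0.05 within each R33 family. In the same edit, list the members of each family and reconcile the 3 and 15 outcomes in the power text with the 13 scores in D.6.c. Keep r=0.43 and r=0.51, labelled as first-step, worst-case detectable values for families of 3 and 15; recompute the value if the listed family has a different size.

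The change needs no extra participants or data and about one line of code. The one drawback is that simple Bonferroni simultaneous confidence intervals would no longer match the tests. The plan does not promise such intervals; if they are wanted, they can be reported with a note that the tests use Holm.
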